Appendix 4: Guideline for Management of Hypertension

Treatment with fostamatinib may cause blood pressure elevation in certain subjects. It is believed that this effect is a result of off-target activity against the VEGFR2 receptor. Increases in BP have proven to be amenable to treatment, generally without a requirement for study drug interruption. **Subjects with elevated blood pressure should receive prompt treatment.**

Blood pressure for all subjects should be kept below 140/90 mmHg; for subjects with increased cardiovascular risk or renal insufficiency, consideration should be given to maintaining the blood pressure below 130/80 mmHg. Subjects should remain on the same dose of ACEi or ARB during the dosing period (Visits 2-9). If additional anti-hypertensive therapy is required, other agents (beta-blockers, calcium channel blockers, or diuretics) should be added. In previous clinical studies evaluating fostamatinib, the following anti-hypertensive agents (alone or in combination) have proven effective in managing BP:

- Angiotensin converting enzyme inhibitors
- Angiotensin receptor blockers
- Calcium channel blockers
- Beta-blockers
- Diuretics

If aggressive and appropriate anti-hypertensive therapy does not control BP (< 140/90), it may be necessary to reduce the dose of study medication.

Management Algorithm for Elevated Blood Pressure

Follow the dose adjustment guidelines in Table 1 when adjusting the dose of study medication.

Table 1: Dose Adjustment

Starting Dose	Dose Level -1	Dose Level -2	Dose Level -3 ^a	Dose Level -4 ^a
100 mg PO bid	150 mg PO qd	100 mg PO qd	Discontinue	-----
150 mg PO bid	100 mg PO bid	150 mg PO qd	100 mg PO qd	Discontinue

^a The Sponsor's Medical Monitor should be consulted prior to consideration of dose modification to levels -3 or -4.

The following should result in prompt discontinuation of study medication:

- The blood pressure cannot be brought under control despite best efforts at blood pressure management.

If BP \geq 180/110 mmHg at any time after randomisation:

- Temporarily withhold dosing with study drug.
- Adjust anti-hypertensive medications.
- Reassess BP twice weekly.
- If a repeat BP \geq 180/110 mmHg despite adjusted anti-hypertensive treatment, permanently discontinue study drug.
- Increase anti-hypertensive medications until control is established.
- Restart study drug (at a reduced dose, see Table 1) when blood pressure $<$ 140/90 mm Hg.

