If the BP is found to be 160-179 systolic or 100-109 diastolic at any visit after randomisation:

- Continue study drug at assigned dose level.
- Adjust anti-hypertensive therapy.
- Reassess BP twice weekly.
- If, after 1 week, the BP remains \geq 160-179 systolic or \geq 100-109 diastolic despite aggressive antihypertensive therapy, interrupt study drug administration.
- Increase anti-hypertensive medications until control is established.
- Restart study drug (at a reduced dose, see Table 1) when blood pressure $<$ 140/90 mm Hg.

If BP is \geq 140 mmHg systolic and/or \geq 90 mmHg diastolic but below 160 systolic or 100 diastolic at any visit after randomisation:

- Continue study drug at assigned dose level.
- Repeat blood pressure assessment within 1 week.
- If blood pressure remains above \geq 140 mmHg systolic and/or \geq 90 mmHg diastolic after 1 week adjust antihypertensive therapy.
- Continue to monitor BP weekly until control is established.
- If BP remains \geq 140 mmHg systolic and/or \geq 90 mmHg diastolic for more than 8 weeks, despite aggressive antihypertensive therapy, reduce dose of study drug (see Table 1).

REFERENCES

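### Under no reading of their and/or wording are Protocol Appendix 4's three blood-pressure tiers both complete and mutually exclusive, and the order of dose reduction and discontinuation is not stated

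*Protocol*

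**What the plan says.** Protocol Appendix 4 (Guideline for Management of Hypertension) gives three tiers, from most to least severe.

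- **Top tier:** BP at or above "180/110 mmHg at any time after randomisation". The first instruction is "Temporarily withhold dosing with study drug". Antihypertensives are adjusted and BP is reassessed twice weekly. A repeat reading at that level means permanent discontinuation.
- **Middle tier:** "If the BP is found to be 160-179 systolic or 100-109 diastolic at any visit after randomisation". The first instruction is "Continue study drug at assigned dose level". Antihypertensives are adjusted straight away and BP is reassessed twice weekly. Drug is interrupted if BP is still at that level after 1 week.
- **Lowest tier:** systolic at least 140 and/or diastolic at least 90, "but below 160 systolic or 100 diastolic at any visit after randomisation". Drug continues at the assigned dose and BP is repeated within 1 week. Antihypertensives are adjusted only if BP is still raised then. The dose is reduced after more than 8 weeks uncontrolled.

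Two general statements precede the tiers. One reads "If aggressive and appropriate anti-hypertensive therapy does not control BP (< 140/90), it may be necessary to reduce the dose of study medication". The other lists, as a reason for prompt discontinuation, "The blood pressure cannot be brought under control despite best efforts at blood pressure management".

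The appendix has no rule for a reading whose systolic and diastolic values point to different tiers.

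**The concern.** Systolic and diastolic pressure often point to different severity bands, so a tiered rule must say which component governs. Here each tier joins the two components differently, and the top tier does not say how they are joined. A site following the text literally can place one reading in two tiers, or place a reading of 185 systolic in the mildest tier alone.

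This matters first for safety. Protocol Section 3.5.1 calls BP elevation a well described effect of the drug, and Section 4.4 lists it among the safety parameters of particular interest. Section 7.5.4 records the lowest of three measurements, so a recorded 185 is the lowest of the three.

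The wording can also affect the data. SAP Section 7.6.1 counts uncontrolled hypertension recorded in dose adjustment as an event of special interest. SAP Section 7.4.1 imputes missing Week 24 spot protein/creatinine ratio from the placebo model for fostamatinib subjects who discontinue because of adverse events. A decision to stop rather than reduce can therefore reach the primary analysis. The documents give no basis for estimating how often.

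**Working it through.** The plan has no figure to reproduce here. The check codes the tiers as conditions and applies them to readings. Let S be systolic and D diastolic.

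- **Top:** S ≥ 180 and D ≥ 110 (*both*), or S ≥ 180 or D ≥ 110 (*either*). The text fits each.
- **Middle:** 160 ≤ S ≤ 179 or 100 ≤ D ≤ 109.
- **Lowest:** (S ≥ 140 or D ≥ 90), with the cap S < 160 *or* D < 100 as printed, or alternatively S < 160 *and* D < 100.

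**Step 1: example readings under the four combinations**

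| Reading | Top both, cap or | Top either, cap or | Top both, cap and | Top either, cap and |
|---|---|---|---|---|
| 185/95 | lowest | top + lowest | none | top |
| 145/115 | lowest | top + lowest | none | top |
| 165/95 | middle + lowest | middle + lowest | middle | middle |
| 150/105 | middle + lowest | middle + lowest | middle | middle |
| 185/105 | middle | top + middle | middle | top + middle |

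**Step 2: all raised integer pairs.** Take S from 100 to 220 and D from 60 to 130, with D < S and with S ≥ 140 or D ≥ 90. The counts by band are:

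| | D < 100 | D 100–109 | D ≥ 110 |
|---|---|---|---|
| S < 160 | 800 + 400 = 1,200 | 59 + 58 + … + 50 = 545 | 49 + 48 + … + 29 = 819 |
| S 160–179 | 20 × 40 = 800 | 20 × 10 = 200 | 20 × 21 = 420 |
| S ≥ 180 | 41 × 40 = 1,640 | 41 × 10 = 410 | 41 × 21 = 861 |

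The total is 6,895. The cells where the components disagree give three groups:

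- Middle against lowest: 800 + 545 = 1,345.
- Top against lowest: 1,640 + 819 = 2,459.
- Top against middle: 420 + 410 = 830.

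| Combination | Pairs in two tiers | Pairs in no tier |
|---|---|---|
| Top both, cap or | 1,345 | 0 |
| Top either, cap or | 1,345 + 2,459 + 830 = 4,634 | 0 |
| Top both, cap and | 0 | 2,459 |
| Top either, cap and | 830 | 0 |

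Every row has either an overlap or a gap. Changing the cap from *or* to *and* only moves the problem: 185/95 then has no tier (top *both*), or 185/105 has two (top *either*). These are counts of possible readings, not of patients.

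**Step 3: which reading of 180/110 the protocol favours.** Section 3.5.1 describes severe elevation by joining the systolic and diastolic limits with *and*. That is not a rule for Appendix 4, but it makes the *both* reading credible. With the cap as printed, 185/95 and 145/115 then sit in the lowest tier alone.

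**Step 4: what differs in practice.** For 185/95 and 145/115 the choice is between withholding and continuing drug. For 165/95 and 150/105 both tiers begin by continuing drug. The differences are:

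- antihypertensives adjusted now, or only after a repeat reading;
- reassessment twice weekly, or a repeat within 1 week and then weekly monitoring;
- interruption after 1 week, or dose reduction only after more than 8 weeks.

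**Step 5: reduction and discontinuation.** The reduction sentence is permissive and concerns aggressive, appropriate therapy that does not reach below 140/90. The discontinuation item concerns BP that cannot be controlled despite best efforts. The lowest tier calls for reduction after more than 8 weeks despite aggressive therapy. Nothing says when a subject passes from one instruction to the next.

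**The case against.** The strongest reply is that nobody would use the appendix this way. In ordinary speech, a cap of below 160 systolic or 100 diastolic can mean below both limits. The tiers run from most to least severe, so a clinician would take the first that fits. The document is a guideline, it stresses prompt treatment, and Section 7.9 leaves adverse-event withdrawal to the investigator's judgment. Extreme readings may also be rare. Entry requires BP at or below 130/80, and Section 3.5.1 reports mean rises of about 2–4 mmHg in rheumatoid arthritis trials (about 5–9 with a history of hypertension) and only a few severe elevations.

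Much of this stands as a limit on frequency and practical effect. It does not settle the wording. A first-match rule is not stated, and even with one, 185/95 goes to the top tier under *either* and to the lowest tier (cap as printed) or no tier (cap *and*) under *both*. SAP Appendix C states *and* or *or* for each BP category and assigns the more severe class when several apply, but only for analysis categories, not for patient management.

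A reader might also infer that reduction and discontinuation flatly contradict each other. The documents do not support that. The best-efforts wording appears only in the discontinuation item, the reduction sentence says only that reduction may be needed, and the appendix's dose table is a ladder ending in discontinuation. Escalation is a plausible reading. What remains is that its order is not stated.

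**Conclusion.** The point holds as a wording defect in a safety rule. Of the four ways to read the tiers, none gives each raised BP exactly one tier. Three leave between 830 and 4,634 of 6,895 enumerated pairs in two tiers, and the fourth leaves 2,459 in none. The counts depend on the chosen grid; the existence of overlaps or gaps does not.

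A reader might infer that every overlapping reading leads sites to opposite actions. That is too strong. Withholding against continuing is at stake only where the top tier is in question, as with 185/95 and 145/115. Readings such as 165/95 and 150/105 get the same first instruction in both tiers and differ in later steps. Nor do the documents show that sites have acted differently or that results have been affected. They show only that the text permits it, in a trial planned for 25 sites in 8 countries.

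The reduction-versus-discontinuation point is secondary and amounts to an unstated sequence. No sample-size, power or type I error figure is affected.

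**What to change.** Reconcile the Appendix 4 passages so that every systolic/diastolic pair falls in exactly one tier. State *and* or *or* for all three tiers, and say how a reading is handled when its components point to different tiers. Check the revised wording against 185/95, 145/115, 165/95, 150/105 and 185/105. State also how the permissive reduction sentence, the reduction after more than 8 weeks and the prompt-discontinuation item relate to one another. The thresholds, the actions and their order are for the sponsor's clinicians to decide.

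The cost is a wording clarification or a letter to sites. It remains useful after main-study dosing ends, because Protocol Section 7.11 applies the Section 7.4 dose-adjustment procedures, and through them Appendix 4, to extended treatment.

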Appendix 5: Restricted Medications

Subjects taking fostamatinib may be affected by drug-drug interactions.

Fostamatinib is metabolized by CYP3A4. In the presence of a strong inhibitor of CYP3A4, the systemic exposure of the active metabolite of fostamatinib may be increased significantly. **Strong inhibitors of CYP3A should not be co-administered with fostamatinib.** Inducers of CYP3A4 may lower concentrations of active drug, possibly to sub-therapeutic concentrations, and their use in subjects taking fostamatinib should be limited.

Fostamatinib is an *in vitro* inhibitor of P-glycoprotein and affects digoxin bioavailability by inhibiting P-gp. If a subject requires digoxin or is taking digoxin concurrently with fostamatinib, digoxin levels should be monitored carefully according to local practice, as the digoxin dose may need to be lowered.

Fostamatinib is known to increase the plasma concentration of the HMG-CoA reductase inhibitors simvastatin and rosuvastatin by 50-100%. If a subject develops muscle pain or weakness, the dose of HMG-CoA reductase may need to be lowered and the subject monitored closely for any adverse effects associated with myositis.

Subjects' concomitant medications should be examined for additional possible drug-drug interactions.

List of Inhibitors and Inducers of CYP3A4

The list below is not an exhaustive list (the Sponsor's Medical Monitor should be consulted in the event of questions).

Strong Inhibitors of CYP3A4

Clarithromycin	Telithromycin	Ketoconazole
Itraconazole	Fluvoxamine	Nefazodone
Ritonavir	Indinavir	Nelfinavir
Sequinavir	Atazanavir	

Moderate Inhibitors of CYP3A

Amiodarone	Aprepitant	Erythromycin
Troleandomycin	Fluconazole	Imatinib
Verapamil	Diltiazem	Amprenavir
Fosamprenavir	Grapefruit juice	Seville oranges
Star fruit		

CYP3A Inducers

Barbiturates

Pioglitazone

Carbamazepine

St. John's Wort

Efavirenz

Rifampin

Phenytoin

Nevaripine

Rifabutin

Modafinil

- To assess the efficacy of fostamatinib administered orally for 24 weeks to subjects with IgA nephropathy, as measured by change in renal function and histology.
- To investigate the safety and tolerability of fostamatinib administered orally for 24 weeks to subjects with IgA nephropathy.

[figure not shown]
3. Study Design

3.1 General Description

This is a Phase 2, multi-center, randomized, double-blind, ascending-dose, placebo-controlled, proof-of-concept study to evaluate 2 dose regimens of fostamatinib in approximately 75 subjects. The study will consist of 11 visits over 28 to 43 weeks.

The study consists of 3 phases: a screening phase, a double-blinded treatment phase and a follow-up phase. Figure 1 presents the study design.

Figure 1: Study Design

Subjects who meet all inclusion/no exclusion criteria will be required to have completed at least 90 days of treatment with either an angiotensin converting enzyme inhibitor (ACEi) or angiotensin II receptor blocker (ARB) at the maximum approved (or tolerated) dose, and to have had a pre-study renal biopsy no more than 180 days prior to randomization (more than 180 days may be approved by the medical monitor on an individual basis). The renal biopsy will be reviewed by a member of the central panel of renal pathologists to ensure subjects meet histological entry criteria (complete scoring by the full panel will occur following randomization).

The enrollment plan for this study is to randomize patients in an ascending dose fashion. Once randomization of the initial cohort of 38 subjects (approximately 25 randomized to fostamatinib 100 mg bid, 13 to placebo) is complete, screening may begin for the second cohort of approximately 37 subjects (approximately 25 randomized to fostamatinib 150 mg bid, 12 to placebo). All subjects in Cohort 2 (150 mg bid or placebo) will be required to have proteinuria >1 gm/day (USA only) or > 0.5 gm/day (rest of the world) at Screening Visit 1b. Subjects will be randomized 2:1 in each cohort to maintain 1:1:1 allocation for all 3 double-blind dosing groups (25 subjects per group: see Table 1). Randomization will be stratified among the 3 treatment groups by presence or absence of endocapillary hypercellularity, as determined by a member of the central panel of renal pathologists on the most recent pre-study renal biopsy obtained prior to randomization (see Figure 1).

During the 24-week double-blind treatment period, subjects should remain on the same dose of angiotensin converting enzyme inhibitor (ACEi) or angiotensin II receptor blocker (ARB) during the treatment period (Visits 2 – 9). Subjects will be monitored by routine safety assessments (vital signs, hematology, serum chemistries, urinalyses, and adverse event (AE) assessments) and for renal function. At the end of the treatment period, a renal biopsy will be obtained.

3.2 Determination of Sample Size

A sample size of 25 evaluable subjects in each of the 3 treatment groups will have an 80% power to detect a 43% reduction in sPCR from Baseline to Week 24 between the pooled fostamatinib and placebo groups, using a 2-sided t-test with $\alpha = 0.05$ and log-transformed data. This calculation assumes that the 3 treatment groups have the same mean and standard deviations of urinary protein/creatinine ratio and coefficient of variation of 0.923 at Baseline and that the values for the placebo group remain constant over 24 weeks. Treatment allocation ratio will be 1:2 for the placebo: combined fostamatinib groups

Table 1 Study Treatment

Treatment Group	Number of Subjects	Dose
C	25	Placebo bid
A	25	Fostamatinib 100 mg bid
B	25	Fostamatinib 150 mg bid

3.3 Methods of Assigning Subjects to Treatment

An Interactive Web Response System (IWRS) will be used to randomize subjects to 1 of 2 groups in each cohort. The IWRS will assign numbered blister packs of study drug to each subject who is eligible for the double-blind treatment period of the study. Randomization will be stratified by the presence or absence of endocapillary hypercellularity at pre-study renal biopsy.

In the event of a medical emergency, when management of a subject's condition requires knowledge of the study drug, the subject's treatment may be unblinded to disclose the identity of the study drug dispensed. Investigators seeking to unblind the subject's treatment assignment will contact the Rigel Medical Monitor who will utilize the IWRS if unblinding is considered warranted. The IWRS will record the reason for unblinding, the name of the user account that performed the unblinding, and the date and time of the unblinding on the unblinding confirmation.

4. Study Endpoints and Covariates

4.1 Demographic and Baseline Characteristics

The demographics characteristics include: age, sex, race, height (cm), weight (kg), and body mass index (kg/m²).

The baseline characteristics include: endocapillary hypercellularity (present vs absent), spot urine protein/creatinine ratio, mesangial hypercellularity score, estimated glomerular filtration rate.

4.2 Primary Efficacy Endpoint

The primary efficacy endpoint is the mean change from Baseline of proteinuria, as measured by sPCR at Week 24.

4.3 Secondary Efficacy Endpoints

The following are the secondary efficacy endpoints considered for this study:

- Spot protein to creatinine ratio (sPCR):
 - Mean change from Baseline of sPCR at Week 12
 - Percentage of subjects with $\geq 30\%$ reduction in sPCR from Baseline at Week 24
 - Percentage of subjects with $\geq 50\%$ reduction in sPCR from Baseline at Week 24
 - Percentage of subjects with sPCR < 500 mg/g at Week 12
- Estimated glomerular filtration rate (eGFR):
 - Mean change from Baseline of eGFR (mL/min/1.73 m²) at Week 12
 - Mean change from Baseline of eGFR (mL/min/1.73 m²) at Week 24
- Haematuria (dipstick test):
 - Shift in haematuria (dipstick test) from baseline to Week 12
 - Shift in haematuria (dipstick test) from baseline to Week 24
- Biopsy Endpoints:
 - Mean change from pre-treatment to post-treatment in mesangial hypercellularity score (sum of mesangial scores/number of scoreable glomeruli) on renal biopsies
 - Shift in M Oxford Classification from pre-study renal biopsy to post-treatment renal biopsy
 - Mean change from pre-treatment to post-treatment in endocapillary hypercellularity score (sum of endocapillary scores/number of scoreable glomeruli) on renal biopsies
 - Shift in E Oxford Classification from pre-study renal biopsy to post-treatment renal biopsy

- Mean change from pre-treatment to post-treatment in cellular/fibrocellular crescent score (sum of cellular/fibrocellular crescent scores/number of scoreable glomeruli) on renal biopsies
- Mean change from pre-treatment to post-treatment in segmental sclerosis/adhesion score on renal biopsies (sum of segmental sclerosis/adhesion scores/number of scoreable glomeruli)
- Mean change from pre-treatment to post-treatment in global glomerulosclerosis score on renal biopsies (sum of global sclerosis scores/number of scoreable glomeruli)
- Mean change from pre-treatment to end of post-treatment in tubulointerstitial scarring on renal biopsies

4.4 Safety Endpoints

The following safety endpoints will be used to assess the safety and tolerability of fostamatinib:

- Incidence of adverse events
- Clinical laboratory results (hematology, serum chemistry, and urinalysis)
- Vital signs
- Physical examinations.

Safety parameters of interest will include increases in blood pressure, adverse effects on liver function tests including transaminase elevations, diarrhea, other GI symptoms and neutropenia.

4.5 Pharmacokinetic Endpoints

The pharmacokinetic endpoint of this study will be a preliminary assessment of the kinetics of fostamatinib in subjects with IgA nephropathy. Plasma concentrations of R406 will be obtained from samples collected at random during study visits (time from last dose will be collected for each sample).

4.6 Exploratory Immunohistochemistry Endpoints

Mean number of macrophages per scoreable glomerulus and the change from baseline will be summarized using descriptive statistics for both extra capillary CD68 macrophages and endocapillary CD68 macrophages.

Change from pre-treatment to post-treatment Syk, Phospho-Syk, Smad 6, and Smad 7 will be evaluated.

This immunohistochemistry analysis will occur once after all samples have been collected. Pathologists performing the analysis will remain blinded to individual treatment assignments until completion of the analysis.

5. Analysis Populations and Subgroup

5.1 Intent-to-Treat Population

The Intent-to-Treat (ITT) population will include all randomized subjects. All efficacy endpoints will be analyzed using the ITT population. Subjects will be analyzed according to their randomized treatment assignment. The efficacy analyses in the ITT population will be considered the primary efficacy analyses.

5.2 Safety Population

The safety population will include all randomized subjects who received any amount of the allocated study drug. The safety population will be analyzed for all safety assessments. The subjects will be analyzed per the treatment they received.

